11. MEASUREMENT OF EFFECT

11.1. Multiple Myeloma Response Assessment

Although the clinical benefit of KRT-232 (AMG 232) has not yet been established, the intent of offering this treatment is to provide a possible therapeutic benefit in combination with KRD, and thus the subject will be carefully monitored for tumor response and symptom relief in addition to safety and tolerability. Subjects with measurable disease will be assessed by standard criteria. Responses levels, including MRD-negative, sCR, CR, VGPR, PR, MR, SD, and progressive disease will be determined by the IMWG Uniform Response Criteria as per Appendix F (Kumar et al., 2016). For the purposes of this study, subjects should be re-evaluated for response every 4 weeks. In addition to a baseline myeloma laboratory testing, confirmatory myeloma laboratory assessment will also be obtained within 4 weeks following initial documentation of an objective response.

11.2. Other Response Parameters

N/A

12. STUDY OVERSIGHT AND DATA REPORTING / REGULATORY REQUIREMENTS

Adverse event lists, guidelines, and instructions for AE reporting can be found in Section 7.0 (Adverse Events: List and Reporting Requirements).

12.1. Study Oversight

This protocol is monitored at several levels, as described in this section. The Protocol Principal Investigator is responsible for monitoring the conduct and progress of the clinical trial, including the ongoing review of accrual, subject-specific clinical and laboratory data, and routine and serious adverse events; reporting of expedited adverse events; and accumulation of reported adverse events from other trials testing the same drug(s). The Protocol Principal Investigator and statistician have access to the data at all times through the CTMS web-based reporting portal.

For the Phase 1 portion of this study, all decisions regarding dose escalation/expansion/de-escalation require sign-off by the Protocol Principal Investigator through the CTMS/IWRS. In addition, for the Phase 1 portion, the Protocol Principal Investigator will have at least monthly,

or more frequently, conference calls with the Study Investigators and the CTEP Medical Officer(s) to review accrual, progress, and adverse events and unanticipated problems.

All Study Investigators at participating sites who register/enroll subjects on a given protocol are responsible for timely submission of data via Medidata Rave and timely reporting of adverse events for that particular study. This includes timely review of data collected on the electronic CRFs submitted via Medidata Rave.

All studies are also reviewed in accordance with the enrolling institution's data safety monitoring plan.

12.2. Data Reporting

Medidata Rave is a clinical data management system being used for data collection for this trial/study. Access to the trial in Rave is controlled through the CTEP-IAM system and role assignments. To access Rave via iMedidata:

- Site staff will need to be registered with CTEP and have a valid and active CTEP-IAM account, and
- Assigned one of the following Rave roles on the relevant Lead Protocol Organization (LPO) or Participating Organization roster at the enrolling site: Rave CRA, Rave Read Only, Rave CRA (LabAdmin), Rave SLA, or Rave Investigator. Refer to <https://ctep.cancer.gov/investigatorResources/default.htm> for registration types and documentation required.
 - o To hold Rave CRA or Rave CRA (Lab Admin) role, site staff must hold a minimum of an AP registration type,
 - o To hold Rave Investigator role, the individual must be registered as an NPIVR or IVR, and
 - o To hold Rave Read Only role, site staff must hold an Associates (A) registration type.

Upon initial site registration approval for the study in Regulatory Support System (RSS), all persons with Rave roles assigned on the appropriate roster will be sent a study invitation e-mail from iMedidata. To accept the invitation, site staff must log in to the Select Login (<https://login.imedidata.com/selectlogin>) using their CTEP-IAM username and password, and click on the accept link in the upper right-corner of the iMedidata page. Site staff will not be able to access the study in Rave until all required Medidata and study specific trainings are completed. Trainings will be in the form of electronic learnings (eLearnings), and can be accessed by clicking on the link in the upper right pane of the iMedidata screen. If an eLearning is required and has not yet been taken, the link to the eLearning will appear under the study name in iMedidata instead of the Rave EDC link; once the successful completion of the eLearning has been recorded, access to the study in Rave will be granted, and a Rave EDC link will display under the study name.

Site staff that have not previously activated their iMedidata/Rave account at the time of initial site registration approval for the study in RSS will also receive a separate invitation from iMedidata to activate their account. Account activation instructions are located on the CTSU website in the Rave section under the Rave resource materials (Medidata Account Activation and

Study Invitation Acceptance). Additional information on iMedidata/Rave is available on the CTSU members' website in the Data Management > Rave section at www.ctsu.org/RAVE/ or by contacting the CTSU Help Desk at [name] or by e-mail at [contact].

Method

This study will be monitored by the Clinical Trials Monitoring Service (CTMS). Data will be submitted to CTMS at least once every two weeks via Medidata Rave (or other modality if approved by CTEP). Information on CTMS reporting is available at <http://www.theradex.com/clinicalTechnologies/?National-Cancer-Institute-NCI-11>. On-site audits will be conducted three times annually (one annual site visit and two data audits). For CTMS monitored studies, after users have activated their accounts, please contact the Theradex Help Desk at [contact] or by email at [contact] for additional support with Rave and completion of CRFs.

Responsibility for Data Submission

For ETCTN trials, it is the responsibility of the PI(s) at the site to ensure that all investigators at the ETCTN Sites understand the procedures for data submission for each ETCTN protocol and that protocol specified data are submitted accurately and in a timely manner to the CTMS via the electronic data capture system, Medidata Rave.

Data are to be submitted via Medidata Rave to CTMS on a real-time basis, but no less than once every 2 weeks. The timeliness of data submissions and timeliness in resolving data queries will be tracked by CTMS. Metrics for timeliness will be followed and assessed on a quarterly basis. For the purpose of Institutional Performance Monitoring, data will be considered delinquent if it is greater than 4 weeks past due.

Data from Medidata Rave and CTEP-AERS is reviewed by the CTMS on an ongoing basis as data is received. Queries will be issued by CTMS directly within Rave. The queries will appear on the Task Summary Tab within Rave for the CRA at the ETCTN to resolve. Monthly web-based reports are posted for review by the Drug Monitors in the IDB, CTEP. Onsite audits will be conducted by the CTMS to ensure compliance with regulatory requirements, GCP, and NCI policies and procedures with the overarching goal of ensuring the integrity of data generated from NCI-sponsored clinical trials, as described in the ETCTN Program Guidelines, which may be found on the CTEP (http://ctep.cancer.gov/protocolDevelopment/electronic_applications/adverse_events.htm) and CTSU websites.

An End of Study CRF is to be completed by the PI, and is to include a summary of study endpoints not otherwise captured in the database, such as (for phase 1 trials), the recommended phase 2 dose (RP2D), and a description of any dose-limiting toxicities (DLTs). CTMS will utilize a core set of eCRFs that are Cancer Data Standards Registry and Repository (caDSR) compliant (<http://cbiit.nci.nih.gov/ncip/biomedical-informatics-resources/interoperability-and-semantics/metadata-and-models>). Customized eCRFs will be included when appropriate to meet

unique study requirements. The PI is encouraged to review the eCRFs, working closely with CTMS to ensure prospectively that all required items are appropriately captured in the eCRFs prior to study activation. CTMS will prepare the eCRFs with built-in edit checks to the extent possible to promote data integrity.

CDUS data submissions for ETCTN trials activated after March 1, 2014, will be carried out by the CTMS contractor, Theradex. CDUS submissions are performed by Theradex on a monthly basis. The trial's lead institution is responsible for timely submission to CTMS via Rave, as above.

The study data manager listed on the protocol face page is responsible for logging the TP53-wild type status confirmation report regardless of test result into the routine reporting system used by Theradex Oncology. This confirmed eligibility report must be sent by email to the submitting physicians/Principal Investigators/Clinical Trials Operations Offices per normal routine and kept on file by the coordinating site per normal routine for audit.

Further information on data submission procedures can be found in the ETCTN Program Guidelines (http://ctep.cancer.gov/protocolDevelopment/electronic_applications/adverse_events.htm).

Data Quality Portal

The Data Quality Portal (DQP) provides a central location for site staff to manage unanswered queries and form delinquencies, monitor data quality and timeliness, generate reports, and review metrics.

The DQP is located on the CTSU members' website under Data Management. The Rave Home section displays a table providing summary counts of Total Delinquencies and Total Queries. DQP Queries, DQP Delinquent Forms, and the DQP Reports modules are available to access details and reports of unanswered queries, delinquent forms, and timeliness reports. Review the DQP modules on a regular basis to manage specified queries and delinquent forms.

The DQP is accessible by site staff that are rostered to a site and have access to the CTSU website. Staff that have Rave study access can access the Rave study data using a direct link on the DQP.

To learn more about DQP use and access, click on the Help icon displayed on the Rave Home, DQP Queries, and DQP Delinquent Forms modules.'

Note: Some Rave protocols may not have delinquent form details or reports specified on the DQP. A protocol must have the Calendar functionality implemented in Rave by the Lead Protocol Organization (LPO) for delinquent form details and reports to be available on the DQP. Site staff should contact the LPO Data Manager for their protocol regarding questions about Rave Calendaring functionality.

12.3. CTEP Multicenter Guidelines

N/A

12.4. Collaborative Agreements Language

The agent(s) supplied by CTEP, DCTD, NCI used in this protocol is/are provided to the NCI under a Collaborative Agreement (CRADA, CTA, CSA) between the Pharmaceutical Company(ies) (hereinafter referred to as "Collaborator(s)") and the NCI Division of Cancer Treatment and Diagnosis. Therefore, the following obligations/guidelines, in addition to the provisions in the "Intellectual Property Option to Collaborator" (http://ctep.cancer.gov/industryCollaborations2/intellectual_property.htm) contained within the terms of award, apply to the use of the Agent(s) in this study:

1. Agent(s) may not be used for any purpose outside the scope of this protocol, nor can Agent(s) be transferred or licensed to any party not participating in the clinical study. Collaborator(s) data for Agent(s) are confidential and proprietary to Collaborator(s) and shall be maintained as such by the investigators. The protocol documents for studies utilizing Agents contain confidential information and should not be shared or distributed without the permission of the NCI. If a copy of this protocol is requested by a subject or subject's family member participating on the study, the individual should sign a confidentiality agreement. A suitable model agreement can be downloaded from: <http://ctep.cancer.gov>.
2. For a clinical protocol where there is an investigational Agent used in combination with (an)other Agent(s), each the subject of different Collaborative Agreements, the access to and use of data by each Collaborator shall be as follows (data pertaining to such combination use shall hereinafter be referred to as "Multi-Party Data"):
 - a. NCI will provide all Collaborators with prior written notice regarding the existence and nature of any agreements governing their collaboration with NCI, the design of the proposed combination protocol, and the existence of any obligations that would tend to restrict NCI's participation in the proposed combination protocol.
 - b. Each Collaborator shall agree to permit use of the Multi-Party Data from the clinical trial by any other Collaborator solely to the extent necessary to allow said other Collaborator to develop, obtain regulatory approval or commercialize its own Agent.
 - c. Any Collaborator having the right to use the Multi-Party Data from these trials must agree in writing prior to the commencement of the trials that it will use the Multi-Party Data solely for development, regulatory approval, and commercialization of its own Agent.
3. Clinical Trial Data and Results and Raw Data developed under a Collaborative Agreement will be made available to Collaborator(s), the NCI, and the FDA, as appropriate and

unless additional disclosure is required by law or court order as described in the IP Option to Collaborator (http://ctep.cancer.gov/industryCollaborations2/intellectual_property.htm).

Additionally, all Clinical Data and Results and Raw Data will be collected, used and disclosed consistent with all applicable federal statutes and regulations for the protection of human subjects, including, if applicable, the *Standards for Privacy of Individually Identifiable Health Information* set forth in 45 C.F.R. Part 164.

4. When a Collaborator wishes to initiate a data request, the request should first be sent to the NCI, who will then notify the appropriate investigators (Group Chair for Cooperative Group studies, or PI for other studies) of Collaborator's wish to contact them.

5. Any data provided to Collaborator(s) for Phase 3 studies must be in accordance with the guidelines and policies of the responsible Data Monitoring Committee (DMC), if there is a DMC for this clinical trial.

6. Any manuscripts reporting the results of this clinical trial must be provided to CTEP by the Group office for Cooperative Group studies or by the principal investigator for non-Cooperative Group studies for immediate delivery to Collaborator(s) for advisory review and comment prior to submission for publication. Collaborator(s) will have 30 days from the date of receipt for review. Collaborator shall have the right to request that publication be delayed for up to an additional 30 days in order to ensure that Collaborator's confidential and proprietary data, in addition to Collaborator(s)'s intellectual property rights, are protected. Copies of abstracts must be provided to CTEP for forwarding to Collaborator(s) for courtesy review as soon as possible and preferably at least three (3) days prior to submission, but in any case, prior to presentation at the meeting or publication in the proceedings. Press releases and other media presentations must also be forwarded to CTEP prior to release. Copies of any manuscript, abstract and/or press release/ media presentation should be sent to:

Email: [contact]

The Regulatory Affairs Branch will then distribute them to Collaborator(s). No publication, manuscript or other form of public disclosure shall contain any of Collaborator's confidential/proprietary information.

12.5. Genomic Data Sharing Plan

N/A

13. STATISTICAL CONSIDERATIONS

13.1. Analysis Sets

13.1.1. Enrolled Analysis Set

The enrolled analysis set will include all subjects who signed an ICF and were enrolled in either the Dose Escalation part or Dose Expansion part of the study.

13.1.2. Full Analysis Set

The full analysis set will include all subjects enrolled in the Dose Escalation part or the Dose Expansion part who received any amount of KRT-232 (AMG 232) and who had at least 1 post-baseline disease assessment.

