4.4. General Guidelines

Following registration, subjects should begin protocol treatment within 14 days. Issues that would cause treatment delays should be discussed with the Principal Investigator. If a subject does not receive protocol therapy following registration, the subject's registration on the study may be canceled. The Study Coordinator should be notified of cancellations as soon as possible.

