13.1.3. Primary Analysis Set

The primary analysis set will include all subjects in the full analysis set who were biomarker positive.

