13.6. Efficacy Analysis

Efficacy analysis will be performed for all subjects in the dose escalation and dose expansion part of the study. Separate efficacy analyses will be performed on the *full analysis set* which includes all subjects enrolled on study, and the *primary analysis set* which includes only subjects who were biomarker positive (*TP53* WT). Parameters assessed will include minimal residual

disease (MRD) negative, stringent complete response (sCR), complete response (CR), very good partial response (VGPR), and partial response (PR), minimal response (MR) and stable disease (SD) per IMWG Uniform Response criteria. In addition, overall response rate (defined as greater than or equal to PR across all cycles of treatment), response duration, time-to-response (TTR), PFS, and OS will be assessed.

Best overall response categories will be tabulated by dose cohort and overall for the IMWG categories of MRD-negative, sCR, CR, VGPR, PR, MR, SD, progressive disease. A two-sided 95% exact binomial CI will be calculated for each category. The myeloma response rate (responses \geq PR) will also be tabulated by dose cohort and overall. Time-to-event analyses will be done using Kaplan-Meier analyses and will include time to response, duration of response, progression-free survival (PFS), and overall survival (OS), as data allow. If there is not enough data to apply the Kaplan-Meier test, the data will be summarized by descriptive statistics.

Time to response (for responders only) will be calculated as the time from the date of first study treatment dosing to the first date of documented response (PR or better) based on IMWG uniform response criteria. Time to response will be summarized by descriptive statistics by dose cohorts.

Duration of response (for responders only) is defined as the time from the earliest date of documented response (PR or better, based on IMWG uniform response criteria) to the earliest date when disease progression was confirmed. Subjects who are non-responders will be excluded from this analysis. Detailed censoring rules for duration of response will be specified in the SAP.

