PFS will be calculated as the time from the time of enrollment until documented disease progression, as determined by the Investigator using IMWG uniform response criteria, or death from any cause, whichever occurs first. Kaplan-Meier methods will be used to estimate PFS over time and the median duration of PFS. Subjects with no PFS event will be censored at the date of their last myeloma disease assessment.

OS is defined as the time from the initial administration of KRT-232 (AMG 232) + KRd to death from any cause. Kaplan-Meier methods will be used to estimate the OS function. Subjects who do not die will be censored at the date that the subject was last known to be alive.

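### The full analysis set has two incompatible definitions, and the one in 13.1.2 drops treated subjects who die or leave before a first disease assessment

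*Combined protocol and SAP*

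**What the plan says.** Section 13.1.2 limits the full analysis set to subjects enrolled in either part "who received any amount of KRT-232 (AMG 232) and who had at least 1 post-baseline disease assessment". Section 13.6, repeated in the synopsis under Statistical Considerations, says the efficacy analyses run on the full analysis set, "which includes all subjects enrolled on study", and on the primary analysis set of TP53 wild-type subjects.

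The wider group already has its own name. Section 13.1.1 defines the enrolled analysis set as "all subjects who signed an ICF and were enrolled in either the Dose Escalation part or Dose Expansion part of the study". Section 13.1.3 builds on the disputed set: "The primary analysis set will include all subjects in the full analysis set who were biomarker positive".

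For time-to-event endpoints, 13.6 counts progression "or death from any cause, whichever occurs first" as a PFS event, timed from enrollment, and adds: "Subjects with no PFS event will be censored at the date of their last myeloma disease assessment". For survival, "OS is defined as the time from the initial administration of KRT-232 (AMG 232) + KRd to death from any cause". The only matter 13.6 leaves to a later SAP is censoring for duration of response. Set membership is not deferred, and no rule says how ORR treats a subject with no assessment.

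**The concern.** Two groups separate the definitions.

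- **Group (a), enrolled but never treated.** Section 4.4 foresees them ("If a subject does not receive protocol therapy following registration", registration may be cancelled), so even their enrolled status is open. Leaving them out is defensible.
- **Group (b), treated but with no assessment after baseline.** These subjects died, withdrew or were lost early. Leaving them out selects on outcome.

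Neither group can contain a documented responder, so removing them cannot lower ORR. The same data could therefore yield two ORRs, both labelled full analysis set, with the 13.1.2 version never the less favourable. If the choice is left until results are known, it can be made on the results.

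A second inconsistency follows. A group (b) death is a PFS and OS event by the definitions in 13.6, yet the subject is outside the 13.1.2 set. The all-enrolled wording is not clean either: OS starts at first dose, so group (a) has no OS start date.

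**Working it through.** **1. Membership under each wording**

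| Subject | 13.1.2 | 13.6 and synopsis |
|---|---|---|
| Enrolled, never treated (a) | out | in, unless cancelled |
| Treated, no post-baseline assessment (b) | out | in |
| Treated and assessed | in | in |

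The definitions agree only if groups (a) and (b) are both empty.

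**2. The plan's own precision figures.** Section 13.3 gives maximum 95% half-widths of 32% for n = 10 and 25% for n = 16 (10 expansion subjects plus 6 at the MTD). At p = 0.5, 2 × √(0.25/n) gives 31.6% and 25.0%. With 1.96 the results are 31.0% and 24.5%; the exact (Clopper-Pearson) maxima are 31.3% and 25.3%. The stated figures are reproduced.

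**3. Effect on ORR.** Let N be the number enrolled, r the responders, u the number in group (a), m the number in group (b), and k = u + m. The documents do not give k, so it is an assumption.

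Shift = r/(N − k) − r/N = r·k / [N(N − k)]

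Removed subjects are never responders, so r ≤ N − k. The shift therefore runs from 0 (k = 0 or r = 0) to a ceiling of k/N (r = N − k).

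| N | k | r | All enrolled | 13.1.2 | Shift (points) |
|---|---|---|---|---|---|
| 10 | 1 | 5 | 50.0% | 55.6% | 5.6 |
| 10 | 1 | 9 | 90.0% | 100% | 10.0 (ceiling) |
| 10 | 2 | 8 | 80.0% | 100% | 20.0 (ceiling) |
| 16 | 1 | 8 | 50.0% | 53.3% | 3.3 |
| 16 | 1 | 12 | 75.0% | 80.0% | 5.0 |
| 16 | 1 | 15 | 93.75% | 100% | 6.25 (ceiling) |
| 16 | 2 | 12 | 75.0% | 85.7% | 10.7 |
| 16 | 2 | 14 | 87.5% | 100% | 12.5 (ceiling) |
| 40 | 1 | 20 | 50.0% | 51.3% | 1.3 |

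For the pooled analysis of 25 to 40 subjects, the ceiling at k = 1 is 1/25 = 4.0 to 1/40 = 2.5 points. For a single dose cohort of 3 to 6 subjects it is 1/3 = 33.3 to 1/6 = 16.7 points.

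Exact 95% intervals for 12 responders: 12/16, 47.6 to 92.7%; 12/15, 51.9 to 95.7%; 12/14, 57.2 to 98.2%.

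With u = 0, every row of the table is also the shift from an all-treated denominator to the 13.1.2 denominator.

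**4. Effect on PFS and OS.** One group (b) death, before any censoring, puts both Kaplan-Meier curves at 15/16 = 93.75% (N = 16) or 9/10 = 90.0% (N = 10) from that time. Under 13.1.2 that event is absent.

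**5. How large group (b) could be.** Section 11.1 re-evaluates response every 4 weeks, so the exposed window is about the first cycle. Both calendars (10.1, 10.2) also schedule myeloma laboratory tests at End of Treatment, so most early stoppers would still be assessed. Early deaths and losses to follow-up would not.

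**The case against.** The strongest reply is that 13.1 is the definitions section, and that the clause in 13.6 is loose wording meant only to contrast all subjects with the TP53 wild-type subset. On that reading 13.1.2 governs, and correcting 13.6 and the synopsis ends the contradiction. This is a plausible account of intent. It would, however, settle on the definition that selects on outcome, so the ORR and early-death problem would remain.

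It is also fair that the affected group may be empty, that deaths are listed and treated subjects counted in the safety analyses (13.1.5, 13.2.2), and that the pooled shift is small. Those points limit the size but not the direction.

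Two objections bear on the remedy:

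- **PFS origin.** PFS runs from enrollment and OS from first dose, so an all-treated set fits the OS origin better. Section 4.4 expects treatment within 14 days of registration. The same mismatch exists under 13.1.2, which also requires treatment, and PFS stays computable.
- **Living group (b) subjects.** Their last myeloma assessment is the pretreatment one, which may precede enrollment. Censored there, such a subject adds essentially nothing to the curve, but the plan should state the convention.

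**Conclusion.** The concern holds. Two current passages give one named set different members, no text reconciles them, and the primary analysis set inherits the conflict. Following 13.1.2 as written can move ORR only upward or not at all, and it removes deaths that 13.6 counts as events.

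The size depends on k, which the documents do not give. One subject removed shifts ORR by at most 6.25 points at N = 16 and 10 points at N = 10; two shift it by at most 12.5 and 20. All of these lie below the plan's stated half-widths of 25 and 32 points.

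The reach is limited. ORR is secondary in Part B and exploratory in Part A, with no decision threshold attached. Time-to-event analyses are done only as the data permit, and follow-up ends 30 days after removal (5.10), which limits the OS effect. MTD and safety rest on 13.1.4 and 13.1.5 and are unaffected. The wording should be settled before the efficacy analysis.

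**What to change.** Put one definition in 13.1.2, 13.6 and the synopsis: all subjects who received any KRT-232 (AMG 232), with the primary analysis set as its TP53 wild-type subset. Then:

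- Count treated subjects with no post-baseline assessment as non-responders in ORR.
- Keep every treated subject, including early deaths, in PFS and OS under the existing event and censoring rules. Add that a living subject with no post-baseline assessment is censored at time zero for PFS.
- Report the response-assessed subset only as a labelled sensitivity analysis.
- State how many subjects were never treated and how many were treated but unassessed.

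The cost is protocol and SAP wording, with no new data collection. The reported ORR may be slightly less favourable.
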